### 7.2.2.3 PK

Individual study drug concentrations, actual sampling time and actual sampling times relative to second study drug administration time (in hours) will be listed. Drug concentrations with actual sampling times out of time windows per study protocol, will be flagged.

The other analyses on pharmacokinetic data (e.g the modelling) are outside the scope of this SAP and will be described in a separate Data Analysis Plan (DAP).

## 7.3 Other Efficacy Analyses

- Evolution over time in clinical symptoms will be evaluated. The body temperature and respiratory rate (actual values, change from baseline and percent change from baseline) will be summarized descriptively over time. Frequency tabulations will be provided to summarize the feeding, respiratory distress parameters (Wheezing (during inspiration/expiration), lung fields affected, crackles/crepitations, respiratory muscle retractorations (supravascular, intercostal and subcostal) , cough and general appearance of the subject over time. Respiratory rate and body temperature will also be presented graphically in mean  $\pm$  SE plots (excluding the in-hospital post-treatment timepoints).
- Respiratory Distress Assessment Instrument (RDAI) and Respiratory Change Score (RACS) will be calculated (see Section 14.2.3 and 14.2.4 for calculation method, respectively) . Actual values (RDAI, RACS) and changes from baseline (RDAI) will be summarized over time using descriptive statistics (both subitem and totals). RDAI, change from baseline in RDAI and RACS will also be presented graphically in mean  $\pm$  SE plots (excluding the in-hospital post-treatment timepoints). Similar to GSS, bar charts will be generated for RDAI to visualize contributing subitems.
- Length of hospital stay (in days – see section 14.2.9 for calculation method) defined as time between admission and discharge for the initial hospitalization will be summarized as descriptive statistics and using KM estimates. In case of missing discharge information the subject will be censored on date(time) of trial termination.
- The time between first study drug administration and discharge (in days) for the initial hospitalization will be summarized as descriptive statistics and using KM estimates. In case of missing discharge information the subject will be censored on date(time) of trial termination.

- Length of hospital stay for RSV: The time between hospital admission and discharge (in days) excluding prolongation due to SAE other than RSV worsening. Time will be summarized as descriptive statistics and using KM estimates. In case of missing discharge information the subject will be censored on date(time) of trial termination. If needed time will be imputed with 18u00 (see section 14.2.10 for calculation details).
- Duration of severe disease (in hours) defined as the time between hospital admission and achieving clinical response will be summarized using KM estimates. The time to event for subjects with missing data and/or who did not reach the clinical response during the trial will be censored at the last nonmissing assessment of blood oxygen level in the vital signs domain (VSTESTCD=OXYSAT) or assessment of adequate oral feeding (DCTESTCD=FEDADQ).
- A cross-tabulation will present the proportion of subjects on oxygen supplementation at baseline versus post-baseline (i.e., any time between first dose date/time and end of study) per treatment group. Additionally, duration of supplemental oxygen therapy (in hours) defined as total time of reported oxygen supply will be calculated based on concomitant medication (CM) records with coded term 'Oxygen' and summarized descriptively. In case of missing CM information a worst case imputation will be applied (see section 14.2.6 for calculation and imputation rules).
- A cross-tabulation will present the proportion of subjects on feeding support at baseline versus post-baseline (i.e., any time between first dose date/time and end of study) per treatment group. Additionally, duration of feeding support (in hours) defined as total time of reported feeding support will be calculated based on concomitant medication records. In case of missing CM information a worst case imputation will be applied (see section 14.2.7 for calculation and imputation rules).
- Incidence of initiation of invasive and non-invasive ventilation (continuous positive airway pressure, bilevel positive airway pressure and high flow ventilation) as well as incidence of apnea will be tabulated. Additionally, duration of invasive and non-invasive ventilation will be summarized descriptively (in hours - see Section 14.2.8 for calculation method).
- The number and percentage of subjects transferred to ICU and duration of ICU stay (in days – see section 14.2.9 for calculation method) will be summarized using descriptive statistics
- Parent(s)/Caregiver(s) diary assessment will be reported as
  - Frequency tabulation over time (condition as before RSV, severity of cough, severity trouble breathing and severity wheezing).
  - Time to 'Condition as before RSV' will be summarized using KM estimates. Time to will be calculated as the time between first dose and the first occurrence of condition as before RSV. The time to event for subjects with missing data and/or who did not reach event during the trial will be censored at the last nonmissing assessment.

- Based on the individual items collected in the diary, a respiratory symptoms score will be calculated. Respiratory symptoms score will be summarized using descriptive statistics over time. Additionally Mean(SE) plot over time will be generated for the total score and a bar chart will be generated to graphically present the contribution of the subitems to the total score over time (see section 14.2.5. for calculation methods).
- The general health of the child was evaluated by completing a Visual Analogue Scale (VAS). VAS will be described using descriptive statistics (see Section 5.4.1 Summary statistics for details) of actual values over time. Additionally, Mean ( $\pm$ SE) plot will be used to present VAS graphically.
- Incidence of medical visit (at least one visit to doctor, hospital or emergency room as well as separately for each type of medical visit) will be tabulated.

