### 3.2.1. INCLUSION CRITERIA

A subject will be eligible for study participation if he/she meets all of the following criteria at screening and randomization, unless specified otherwise:

1. Subject is a male or female infant or young child aged 28 days to <2 years with gestational age  $\geq$  33 weeks at screening.
2. Subject weighs between  $\geq$  3.0 kg and < 15.0 kg at screening.
3. Subject is otherwise healthy, but is hospitalized for and clinically diagnosed with RSV LRTI (bronchiolitis or broncho-pneumonia), i.e., showing typical clinical signs and symptoms such as tachypnea, wheezing, cough, crackles, use of accessory muscles and/or nasal flaring.
4. Subject has a positive RSV diagnostic test at screening.##
5. Subject is expected to have to stay in the hospital for at least 24 hours (according to the Investigator's judgment at screening).
6. Symptoms likely related to RSV infection (i.e., the symptoms present need to be probably linked to the current RSV infection according to Investigator's judgment) have appeared within 4 days of screening and are not yet improving at screening and randomization.
7. Subject fulfils at least two of the following RSV disease severity criteria at screening and randomization:
  - Inadequate oral feeding that requires feeding support (i.e., nasogastric tube or i.v. line)
  - Inadequate oxygen saturation defined as:
    - Oxygen saturation ( $SpO_2$ )  $\leq$  92% on room air or
    - Requiring oxygen supplementation to maintain oxygen saturation  $>$  90% with documented pre-supplementation value  $\leq$  92%
  - Signs of respiratory distress defined as:
    - Respiratory rate  $\geq$  50 per minute in infants up to 12 months of age, and  $\geq$  40 per minute in children above 12 months and/ or
    - Moderate or marked respiratory muscle retractions

---

## RSV infection will be confirmed either according to routine site practice (PCR or diagnostic quick test), or using a (Sponsor-provided) commercial kit.

8. Subject has normal psychomotor development.
9. Parent(s)/legal guardian(s) provide written informed consent in accordance with locally approved consent process at screening.
10. The parent(s)/legal guardian(s) are able and willing to comply with the study protocol procedures.

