#### 14.2.6 Duration of supplemental oxygen therapy

This is based on concomitant medication records.

For Baseline assessment a subject is considered being on oxygen supplementation at baseline if oxygen was received between hospital admission and the first dose of study medication. For this derivation, both prior and concomitant medications are considered

Total duration will be calculated as the total number of hours (taking into account the sum of the actual time windows the concomitant medication was received) using concomitant treatment coded as "Oxygen" from admission until trial termination and from first dose until trial termination. Missing information on concomitant medication records will be imputed in the following way

- If start time is missing: impute with 0:00 .

- If end time is missing: impute with 23:59.
- If start day/month is missing: impute with first day (01) / month (Jan) if this falls within trial window, otherwise impute with day/month of first contact in the trial.
- If end day/month is missing: impute with last day (31) / month (Dec) if this falls within trial window, otherwise impute with day/month of trial termination.

In case of overlapping records, the duration will be calculated only once for the overlapping part of the records.

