#### 14.2.7 Duration of feeding support

This is based on concomitant medication records.

For Baseline assessment a subject is considered being on feeding support at baseline if support was received between hospital admission and the first dose of study medication. For this derivation, both prior and concomitant medications are considered

Following coded terms will be considered for feeding support provided the route of administration is intravenous or nasogastric.

AMINO ACIDS NOS  
AMINOVEN  
CALCIUM GLUCONATE  
DEXTROSE AND SODIUM CHLORIDE INJECTION  
DEXTROSE IN LACTATED RINGER'S  
ELECTROLYTES NOS  
ELECTROLYTES NOS W/GLUCOSE  
GLUC5% W/RINGER BAXTER  
GLUCOSE  
GLUKOSALINA /06282701/  
INFANT FORMULAS  
ISOLYTE /06504901/  
ISOLYTE P DEXTROSA  
JONOSTERIL /01263001/  
MAGNESIUM SULFATE  
MATERNA /02266601/  
OSMOTAN  
POTASSIUM CHLORIDE  
PROTEIN HYDROLYSATE  
RICE /08368701/  
RINDEX /07339201/  
RINGER-LACTATE

SODIUM CHLORIDE  
SODIUM GLYCEROPHOSPHATE

Total duration will be calculated as the total number of hours (taking into account the sum of the actual time windows the concomitant medication was received) using concomitant treatment from the above list from admission until trial termination and from first dose until trial termination. Missing information on concomitant medication records will be imputed in the following way

- If start time is missing: impute with 0:00 .
- If end time is missing: impute with 23:59.
- If start day/month is missing: impute with first day (01) / month (Jan) if this falls within trial window, otherwise impute with day/month of first contact in the trial.
- If end day/month is missing: impute with last day (31) / month (Dec) if this falls within trial window, otherwise impute with day/month of trial termination.

In case of overlapping records, the duration will be calculated only once for the overlapping part of the records.

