**Table 14.2.6.6: Hospitalisation – Oxygen supply: cross tabulation.**

Cross tabulation of oxygen supply post-baseline versus baseline.

Population: mITT population.

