**Table 14.2.6.7: Hospitalisation – Feeding support: cross tabulation.**

Cross tabulation of feeding support post-baseline versus baseline.

Population: mITT population.

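### The oxygen and feeding-support cross-tabulations in SAP 7.3 cannot show infants coming off support, because anyone on support at first dose is 'post-baseline yes' by definition

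*SAP*

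**What the plan says.** SAP 7.3 (Other Efficacy Analyses) describes two cross-tabulations per treatment group. The first gives the proportion of subjects "on oxygen supplementation at baseline versus post-baseline (i.e., any time between first dose date/time and end of study". The second gives the proportion "on feeding support at baseline versus post-baseline (i.e., any time between first dose date/time and end of study".

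Baseline status is defined in the conventions. Under SAP 14.2.6 a subject is on oxygen at baseline if "oxygen was received between hospital admission and the first dose of study medication". Under SAP 14.2.7 a subject is on feeding support at baseline if "support was received between hospital admission and the first dose of study medication". Neither rule asks whether support was still running at the time of dosing.

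The table index adds no timepoint. Table 14.2.6.6 is described as "Cross tabulation of oxygen supply post-baseline versus baseline" and Table 14.2.6.7 as "Cross tabulation of feeding support post-baseline versus baseline".

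**The concern.** A baseline-by-post-baseline table is normally read as a shift table: the 'yes to no' cell is taken as the infants who came off support. Under these rules that reading is wrong. Support that is running at first dose continues past first dose, if only briefly, so it satisfies the post-baseline rule before the drug can act.

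What is at stake is modest but real. Need for oxygen is among the safety variables in Protocol 3.6.7, and duration of supplemental oxygen is an endpoint in Protocol 3.6.4. For oxygen, these tables are the only planned proportion of infants on support after dosing. SAP 7.3 tabulates feeding over time but not oxygen, and the medical-interventions item of the Global Severity Score (GSS) is summarised with descriptive statistics for a score. A reader of the study report who sees nearly the same 'yes' proportion in every arm could conclude that treatment made no difference to weaning, when the table could not have shown one.

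**Working it through.** The plan states no figure for this point, so there is none to reproduce. The check applies the coding rules and then illustrates their effect.

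**Step 1. The four cells.** Let baseline B = 1 if support was given at any time from admission to first dose, and post-baseline P = 1 if it was given at any time from first dose to end of study.

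| Infant's course | B | P |
|---|---|---|
| On support at first dose, any later duration | 1 | 1 |
| Supported after admission, stopped before dosing, restarted later | 1 | 1 |
| Supported after admission, stopped before dosing, no restart | 1 | 0 |
| Never supported before dosing, started later | 0 | 1 |
| Never supported | 0 | 0 |

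The time at which support ends after dosing appears nowhere in the table. Only pre-dose weaning without restart leads to B = 1, P = 0.

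**Step 2. The baseline-yes row in general.** Let a be the share on support at dosing, w the share weaned between admission and dosing, and r the restart probability in the weaned group. Then

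P(post-baseline yes | baseline yes) = (a + r·w) / (a + w).

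The weaning-time distribution after dosing does not enter. With assumed inputs (the documents give none) and r = 0.2:

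- a = 0.70, w = 0: 0.70/0.70 = 1.00
- a = 0.70, w = 0.05: (0.70 + 0.01)/0.75 = 0.947
- a = 0.50, w = 0.10: (0.50 + 0.02)/0.60 = 0.867

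Simulation with 400,000 infants per arm and median time to coming off of 48 h versus 24 h gave 1.00 v 1.00, 0.947 v 0.946 and 0.866 v 0.867. Cutting the active median to 1 h left the proportions unchanged within simulation error.

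**Step 3. What status at fixed times would show.** Assume exponential remaining time on oxygen among infants on oxygen at first dose, so the proportion still on at t hours is 2^(−t/median). Nominal times are 24 + 5 = 29 h (Day 2, 5 h) and 48 + 2 = 50 h (Day 3, 2 h), ignoring nebulization time and dosing windows.

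| Assumed medians | Time | Still on oxygen | Difference | Planned coding, same infants |
|---|---|---|---|---|
| 48 v 24 h | 29 h | 0.658 v 0.433 | 0.225 | 1.00 v 1.00 |
| 48 v 24 h | 50 h | 0.486 v 0.236 | 0.250 | 1.00 v 1.00 |
| 36 v 18 h | 29 h | 0.572 v 0.327 | 0.245 | 1.00 v 1.00 |

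**Step 4. How many infants this concerns.** Protocol 3.2.1 states "Subject fulfils at least two of the following RSV disease severity criteria at screening and randomization", out of feeding, saturation and respiratory distress. Every eligible infant therefore meets the feeding or the saturation criterion. The feeding criterion requires support. The saturation criterion can be met on room air without supplementation, and feeding support plus respiratory distress qualifies without any oxygen problem. First dose follows within 3 h of randomization. It is plausible that most baseline-yes infants are still on support at dosing, but the documents give no proportion. Step 1 does not depend on it.

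**The case against.** The strongest reply is that other outputs already measure coming off support.

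- SAP 7.3, with 14.2.6 and 14.2.7, reports total hours of oxygen and of feeding support, including from first dose (Tables 14.2.6.4 and 14.2.6.5).
- SAP 7.2.2.1 gives Kaplan-Meier times from first dose to adequate saturation and to adequate oral feeding. The saturation criterion is measured on room air, so it implies being off oxygen.
- Table 14.2.4.5 tabulates feeding by timepoint, including feeding support.
- The protocol endpoint is duration of oxygen, and the SAP analyses it. The cross-tabulations are untested, not flagged for topline, and may be meant only to record any use.

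All of this stands, and it sets the impact at low. It does not repair the two tables: their layout invites a shift reading that the coding makes impossible, and for oxygen no other output gives the proportion on support at scheduled times.

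Three stronger readings are tempting and not supported. First, a reader might infer that the SAP has no way to see an effect on weaning; the outputs above show otherwise. Second, a reader might infer that the arms must look identical, at 100% each. That holds only for infants on support at the moment of dosing. The planned row also contains infants weaned earlier (0.867 and 0.947 in two scenarios above), and new starts and restarts can differ between arms. Third, a reader might assume that the baseline-no group is small; the documents give no figure.

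**Conclusion.** The point holds as a matter of definition for both tables. An infant on support at first dose is always post-baseline 'yes', and 'baseline yes, post-baseline no' contains only pre-dose weaning without restart. The tables can inform on new starts and restarts, not on coming off support.

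The impact is low: descriptive 'other' outputs, with no effect on the primary analysis, alpha or power. The differences of roughly 22 to 25 percentage points that the oxygen table would not show rest wholly on assumed exponential weaning with the stated medians. They illustrate the insensitivity of this table and are not information lost to the trial. The gap is wider for oxygen than for feeding, where status by timepoint is already planned.

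**What to change.** **Oxygen (SAP 7.3, Table 14.2.6.6).** Cross status at the moment of first dose with status at scheduled times, for example Day 2 pre-dose, Day 2 5 h, Day 3 pre-dose, Day 3 2 h and Day 14. Keep an any-new-start-after-first-dose row only for infants not on oxygen at first dose.

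**Feeding support (SAP 7.3, Table 14.2.6.7).** Base baseline status on the moment of first dose, limit the any-time row to new starts, and refer to Table 14.2.4.5 for status by timepoint.

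**Conventions.** Say whether the 23:59 imputation for missing end times, which 14.2.6 and 14.2.7 state for duration, also applies here. If it does, an infant who stopped before dosing on Day 1 with no recorded end time would be counted as still on support at first dose.

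**Cost.** SAP wording and reprogramming of two tables from dated records already used for the duration analyses. No new data are needed. The downside is slightly longer tables.

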#### 7.4 Subgroups Analysis

Subgroups analysis will be performed on the mITT population for the following subgroups:

- Age category: <6 months, 6 - <12 months and  $\geq$ 12 months
- Subjects with inadequate oral feeding and inadequate oxygen saturation at baseline vs other
- Co-infected subjects vs RSV only subjects

The analyses listed below will be performed on the subgroups mentioned above:

- Time to BQL based on the plaque assay summarized using Kaplan Meier estimates
- GSS, summarized using descriptive statistics of the actual values and the change from baseline over time
- Time to clinical response, summarized using Kaplan Meier estimates
- Time between first study drug administration and discharge, summarized using descriptives statistics and Kaplan Meier estimates

Subgroups analyses on subjects with inadequate feeding and inadequate oxygen saturation at baseline and co-infected subjects will be performed if at least 15% of the subjects have inadequate feeding and inadequate oxygen saturation at baseline, and are co-infected; respectively.

## 8 SAFETY

### 8.1 Adverse Events

#### 8.1.1 Definitions

An AE is defined as any untoward medical occurrence in a clinical study subject administered a medicinal (investigational or non-investigational) product. An AE does not necessarily have a causal relationship with the treatment. All AEs will be reported from the time a signed and dated ICF is obtained until completion of the subject's last visit.

A treatment emergent adverse event (TEAE) is defined as any adverse event starting or worsening in severity (for pre-existing conditions) from the start of study drug administration, until completion of the subject's last visit.

All tables will only present TEAE. Pre-treatment AEs will only be listed.

#### 8.1.2 Coding

All adverse events will be coded using the latest version of the Medical Dictionary for Regulatory Activities (MedDRA) available at the time of database lock. The actual version used will be mentioned on AE outputs.

#### 8.1.3 Handling of missing AE information

Generally speaking a conservative approach is used to determine if an AE is treatment emergent in case of missing/partial onset date/time. (see section 14.3.1 for more details)

No imputation will be done of missing/partial date(time) fields. The dates and times will be presented in the listings as captured in the eCRF.

#### 8.1.4 Drug relatedness

Following ICH-E3, the drug relatedness as assessed by investigator will be dichotomized as follows:

- Drug related: at least possibly drug related, or with a missing drug relatedness
- Not drug related: less than possibly drug related.

#### 8.1.5 Calculation of Incidences of AEs

Incidence will be calculated on a subject level as the number (and percentage) of subjects for which the AE (preferred term or system organ class) was at least 1 time reported (within a treatment group) against the total number of subjects (within a treatment group). For the adverse event summary table (see Section 8.1.7) and the general TEAE table (All TEAE by SOC and PT) a separate count representing the number of events will be reported (without percentage).

### 8.1.6 Worst case reporting

When cross tabulating AE preferred terms versus an AE attribute (e.g., severity), the worst-case is always applied. I.e., when a subject has two times the same AE preferred term, then the subject is reported only once: only with the worst severity. A missing severity will not be imputed.

